13.1.3 Statistical Evaluation

Descriptive statistics, such as the mean, standard deviation, median, 25th percentile, 75th percentile, minimum value, and maximum value for quantitative variables, and counts and percentages for categorical variables, will be provided. Key supporting data will be provided in data listings. Summary statistics will be presented by the overall BRV dose.

For the purpose of statistical analysis, the following periods are considered:

- Evaluation Period (V1 until the last Evaluation Visit)
- Down-Titration Period
- Post-Treatment Period

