13.1.3.1 Evaluation of Safety

All safety variables will be analyzed by descriptive methods on the Safety Population. Treatment-emergent adverse events will be summarized by categories of total duration of exposure, period, Medical Dictionary for Regulatory Activities (MedDRA[®]) Primary System

Organ Class and Preferred Term in incidence tables. Separate tables will be provided, by categories of total duration of exposure, for AEs leading to withdrawal from the study and SAEs.

Changes in laboratory values, vital signs, and weight will be summarized by visit. Possibly clinically significant treatment-emergent abnormalities for laboratory values, vital signs, and weight will be listed and summarized by analysis period. Electrocardiogram abnormalities, as well as physical and neurological abnormalities, will be presented in subject data listings.

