### 3.2.4 Study periods

The study is divided into 3 periods: Evaluation Period, Down-Titration Period, and Post-Treatment Period. A subject is classified as “discontinued” if the subject has a termination case report form (CRF) or has an early discontinuation visit (EDV). A subject is classified as “completed” if this subject completes the full extent of the study as defined in the protocol at database lock.

A “discontinued” subject can be potentially slotted into the 3 periods of the study. The following algorithms will be used to slot the subject appropriately into the Evaluation Period, Down-Titration Period, and Post-Treatment Period.

- For Evaluation Period, the start date is the date of first dose of BRV, and the following algorithm is used to determine the end date:
  - If the subject enters the Down-Titration Period, then the date of EDV is the end date;
  - If the subject does not enter the Down-Titration Period but meets 1 of the following criteria, the Evaluation Period ends on date of last dose of BRV:
    - Without an EDV but having a termination CRF,
    - With an EDV and having a termination CRF,
    - With an EDV and the date of EDV prior to the database lock date and having no termination CRF.
- A subject is considered entering Down-Titration Period only if the subject has an EDV and at least 1 dose of study drug after the date of EDV, the start date of Down-Titration Period is set as 1 day after the date of EDV, and the Down-Titration Period ends on date of last dose of BRV. A subject without an EDV but having a termination CRF or with an EDV but without any dosing of study drug after the EDV will not have the Down-Titration Period, and no artificial Down-Titration Period will be created for analysis.
- A subject is considered entering the Post-Treatment Period if the subject has at least 1 contact (scheduled visit, unscheduled visit, or telephone contact) after the date of last dose of BRV. The Post-Treatment Period starts 1 day after date of last dose of BRV irrespective of entering the Down-Titration Period, and there is no end date.

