### 3.2.6 Last value on BRV treatment

Last Value for QOLIE-31-P, HADS, EQ-5D, and socio-professional data is the last assessment strictly after the date of first dose of BRV and up to and including the YEV at the end of the second year and any EDVs for subjects who did not complete through the YEV at the end of the second year.

Last Value for clinical laboratory parameters, vital signs, and ECGs is the last available result obtained after the first dose of BRV and prior to or on the date of last dose of BRV. All scheduled and unscheduled assessments within this time period will be considered. Last Value will be determined separately for each laboratory parameter for hematology, chemistry, and urinalysis assessments.

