### **11.3.1 Hematology and blood chemistry parameters**

Observed values for each planned hematology and blood chemistry parameter will be summarized for Baseline, Study Entry, and each scheduled visit during the Evaluation Period for which laboratory parameters were assessed, Last Value, EDV, and FV. Change from Baseline will be summarized for all post-Baseline time points including EV. Only laboratory parameters planned per protocol will be summarized; results for laboratory parameters not planned per the protocol will only be provided in subject data listings.

The number and percentage of subjects with an on-treatment potentially clinically significant treatment-emergent (PCST) value, PCST low value, and PCST high value will be summarized. This summary will consider all assessments after the first dose of BRV and prior to or on the date of the last dose of BRV. Percentages will be relative to the number of subjects with an on-treatment assessment.

Additionally, the number and percentage of subjects with a PCST value, PCST low value, and PCST high value will be summarized for Baseline, Study Entry, each visit during the Evaluation Period for which laboratory parameters were scheduled to be assessed, EDV, Last Value, and FV. Percentages for each parameter and time point will be relative to the number of subjects with a value at that time point.

PCST (Sections 13.3.1, 13.3.2, and 13.3.3) criteria are based on FDA Division of Neuropharmacologic Drug Products guidelines with some UCB-defined additions.

Creatinine clearance, when available from the central laboratory, will be provided in subject data listings only and will not be summarized.

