## **11.4 Vital Signs, Physical Findings, and Other Observations Related to Safety**

### **11.4.1 Vital signs**

Vital signs are assessed at all FEVs, MEVs, YEVs, EDVs, and at FV, and may also be assessed at Unscheduled Visits. Body weight is assessed at all FEVs, YEVs, EDVs, and at FV, and may also be assessed at Unscheduled Visits.

Observed values for SBP, DBP, pulse rate, and body weight will be summarized for Baseline, Study Entry, each visit during the Evaluation Period for which vital signs or body weight were assessed, EDV, Last Value, and FV. Changes from Baseline for SBP, DBP, pulse rate, and body weight will be summarized for all post-Baseline time points.

The number and percentage of subjects with an on-treatment PCST value, PCST low value, and PCST high value will be summarized for SBP, DBP, pulse rate, and body weight. This summary will consider all assessments after the first dose of BRV and prior to or on the date of the last dose of BRV.

Additionally, the number and percentage of subjects with a PCST value, PCST low value, and PCST high value will be summarized for the above parameters for Study Entry, each visit during the Evaluation Period for which vital signs or body weight were scheduled to be assessed, Last Value, EDV, and FV. Percentages will be relative to the number of subjects with a value at each time point.

PCST criteria (Section 13.3.4) are based on FDA Division of Neuropharmacologic Drug Products guidelines with some UCB-defined additions

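### The SAP drops the protocol's by-period summary of clinically significant laboratory, vital-sign and weight abnormalities without declaring it, so unscheduled tests after the last dose enter no such table

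*SAP*

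**What the plan says.** Protocol 13.1.3.1 states: "Possibly clinically significant treatment-emergent abnormalities for laboratory values, vital signs, and weight will be listed and summarized by analysis period". Protocol 13.1.3 introduces the periods with "For the purpose of statistical analysis, the following periods are considered" and names Evaluation, Down-Titration and Post-Treatment. SAP 3.2.4 keeps them: "The study is divided into 3 periods: Evaluation Period, Down-Titration Period, and Post-Treatment Period". SAP 11.2.2 uses them to tabulate treatment-emergent adverse events (TEAEs).

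The SAP's tables of potentially clinically significant treatment-emergent (PCST) values do not use them. Haematology and chemistry (11.3.1), urinalysis (11.3.2) and vital signs with weight (11.4.1) share two outputs:

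- An on-treatment count of subjects with a PCST value. For laboratory data it takes in "all assessments after the first dose of BRV and prior to or on the date of the last dose of BRV". For vital signs and weight the rule is the same: "This summary will consider all assessments after the first dose of BRV and prior to or on the date of the last dose of BRV".
- A by-visit count with rows for Study Entry, the Evaluation Period visits at which the test was scheduled, EDV, Last Value and FV, plus Baseline for laboratory data.

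SAP 3.2.6 defines the Last Value row: "Last Value for clinical laboratory parameters, vital signs, and ECGs is the last available result obtained after the first dose of BRV", with the same upper limit at the last dose. SAP 2.5, which records changes from the protocol's analysis, mentions only the monotherapy endpoint.

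**The concern.** Long-term safety is the primary objective, and the by-period table is the protocol's only stated summary of these abnormalities. Replacing it without saying so has three effects. A reader of the study report cannot see what arose after stopping as a group. Results during taper cannot be told apart from results during the Evaluation Period. Some post-dose results reach no PCST table at all. The SAP itself foresees unscheduled tests (11.3 and 11.4.1) and defines a post-treatment period in which they can fall, so this case is within the plan's own expectations.

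Protocol 13.3 requires changes from the protocol to be discussed in the study report. A change missing from SAP 2.5 is easily missed there too.

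**Working it through.** The plan gives no figure to reproduce. The check follows each kind of assessment to the PCST outputs.

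**Rules used**

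- The last dose is the last one in any study period, not only in the Evaluation Period (SAP 3.2.1). Doses taken during taper therefore extend the on-treatment window.
- A subject has a Down-Titration Period only with an EDV and at least one dose after it. Without such a dose, the Evaluation Period ends at the last dose (SAP 3.2.4).
- "The Post-Treatment Period starts 1 day after date of last dose of BRV irrespective of entering the Down-Titration Period, and there is no end date" (SAP 3.2.4).

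**Tracing**

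| Assessment | Protocol period | On-treatment count | Last Value | By-visit row |
|---|---|---|---|---|
| Scheduled Evaluation visit | Evaluation | yes | if latest | yes |
| Unscheduled, during Evaluation | Evaluation | yes | if latest | none |
| EDV on or before the last dose | Evaluation | yes | if latest | EDV |
| Unscheduled, during taper | Down-Titration | yes, pooled with Evaluation | if latest | none |
| EDV after the last dose | Post-Treatment | no | no | EDV |
| FV after the drug-free period | Post-Treatment | no | no | FV |
| Unscheduled, after the last dose | Post-Treatment | no | no | none |

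**Reading the table**

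1. None of the three promised period summaries is delivered as such. Two periods are merged and the third is split between the FV row and part of the EDV row.
2. The last line has no entry. Those results are found only in the listings (SAP 3.1), or in an adverse event table if the investigator reports the finding as an adverse event.
3. The EDV row mixes on-drug visits with visits after the last dose.
4. The FV row does not replace a Post-Treatment summary for laboratory data. Table 5:1 allows FV laboratory tests to be omitted when the preceding EDV results were normal, so the subjects in that row are selected. Vital signs and weight at the FV carry no such exemption.

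**Scale**

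SAP 2.4 gives 108 enrolled. One subject is 1/108 = 0.93 percentage points. The PCST denominator is subjects with an on-treatment assessment (SAP 11.3.1). It cannot exceed 108, so one subject weighs at least that much. The number of unscheduled post-dose tests is not stated, so no total effect can be calculated.

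**The case against.** A reader might infer that the headline abnormality rate is biased low in exactly the subjects who stop for safety, for example under the liver-enzyme withdrawal criterion in Protocol 9.3. The documents do not support this. A value that triggers withdrawal normally comes before the last dose and is counted, whether the test was scheduled or not. The count is of subjects, so a later and higher peak in someone already counted changes nothing. The on-treatment count could differ from an all-period count only for a subject whose on-treatment values all stayed below the threshold (3 times the upper limit of normal for AST and ALT, SAP 13.3.2) and who first crossed it afterwards. Even then, an EDV or FV result still abnormal would show in its own row. Saying that one missed case out of two would halve a rate is an invented example.

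A reader might also argue from the half-life of about 8 hours (Protocol 6.2) that a test on the day after stopping still reflects exposure. That figure is for young healthy men, and the SAP defines its window by dosing dates, so the argument does not show the window to be wrong.

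The rest of the opposing case is largely sound. The EDV ordinarily precedes taper and so falls on drug. An abnormal laboratory result at the EDV removes the exemption from FV testing. Abnormal laboratory findings can be adverse events (Protocol 12.1.1), and TEAEs are tabulated by period, although the 3-month-interval TEAE tables also stop at the last dose. Nothing but adverse event recording is scheduled at the Down-Titration Phone Call, so a Down-Titration column would be sparse. All analyses are descriptive.

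These points limit the harm. They do not remove the mismatch, its absence from SAP 2.5, or the empty line in the tracing. Adverse event reporting rests on the investigator's judgement, whereas PCST criteria apply fixed thresholds, so one does not stand in for the other.

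**Conclusion.** The concern holds as an undeclared departure from the protocol with a narrow gap in the tables. The by-period PCST summary is missing for laboratory values, vital signs and weight. Unscheduled assessments after the last dose enter no PCST table, and an EDV after the last dose appears only in the EDV row. This follows from the text alone and needs no assumption about the data.

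The practical effect is unknown and may be small. It depends on how many subjects had an unscheduled test after the last dose and first met a criterion there. The on-treatment count is accurate for what it is labelled and would mislead only if read as the rate over the whole study. No conclusion of the trial is invalidated, but the matter lies in the primary safety domain and should be corrected.

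**What to change.** In SAP 11.3.1, 11.3.2 and 11.4.1, add the number and percentage of subjects with a PCST value (any, low, high) for each of the Evaluation, Down-Titration and Post-Treatment Periods. Use all scheduled and unscheduled assessments. Take subjects with at least one assessment of that parameter in the period as the denominator. Keep the on-treatment count as a further line.

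Footnote that the Down-Titration and Post-Treatment denominators are small and selectively tested, because no laboratory tests are scheduled during taper and FV laboratory tests may be skipped after a normal EDV. Counts should therefore be read before percentages.

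If the sponsor prefers not to restore the table, SAP 2.5 should declare the departure and give the reason, and the study report should repeat it.

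The cost is SAP wording and one extra set of columns in existing tables. The data are already collected, and the period definitions are already needed for the TEAE tables. No visit or procedure changes.

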### 11.3.2 Macroscopic urinalysis

Quantitative urinalysis parameters will be summarized in the same manner as hematology and blood chemistry parameters. Response categories are negative, 1+, 2+, and 3+ for the qualitative urinalysis parameters occult blood, leukocytes, glucose, protein, and ketones and negative and positive for nitrates. Outcome values for these parameters are mapped to the levels Negative, 1+, 2+, and 3+ as follows for purposes of summary tables and the determination of PCST:

| Category | Definition   |
|----------|--|
| Negative | “Negative”, “NEGATIVE”, or other outcomes that clearly reflect a negative finding  |
| 1+       | “1+”, “+”, “Trace”, “TRACE”, or other outcomes that clearly reflect trace amount   |
| 2+       | “2+” or “++”   |
| 3+       | “3+”, “+++”, or other outcomes that clearly reflect the data above 3+ (eg, “4+”, “5+” etc) or more than 4 plus signs (eg, “++++”, “+++++” etc) |

For qualitative urinalysis parameters (occult blood, leukocytes, glucose, protein, ketones, and nitrates), the number and percentage of subjects with each response category will be summarized for Baseline, Study Entry, each scheduled visit during the Evaluation Period for which urinalysis parameters were scheduled to be assessed, Last Value, EDV, and FV. Percentages for each parameter will be relative to the number of subjects with a result at each time point.

For occult blood, leukocytes, glucose, protein, ketones, and nitrates, the number and percentage of subjects with an on-treatment PCST value, PCST low value, and PCST high value will be summarized. This summary will consider all assessments after the first dose of BRV and prior to or on the date of the last dose of BRV. Percentages will be relative to the number of subjects with an on-treatment assessment.

Additionally, for occult blood, leukocytes, glucose, protein, ketones, and nitrates, the number and percentage of subjects with a PCST value, PCST low value, and PCST high value will be summarized for Baseline, Study Entry, each visit during the Evaluation Period for which laboratory parameters were scheduled to be assessed, EDV, Last Value, and FV. Percentages for each parameter and time point will be relative to the number of subjects with a value at that time point.

### 11.3.3 Microscopic urinalysis

In microscopic urinalysis, a small sample of urine is centrifuged to remove the liquid. The sediment is then examined under a microscope. In the urinalysis laboratory test group, other than urinalysis parameters such as Bilirubin, Blood, Glucose, Ketone, Nitrite, pH, Protein, Specific Gravity, Total protein, Occult Blood, and Leukocytes, a listing of microscopic analysis parameters will be provided; no summaries of microscopic analysis findings are planned.

## **11.4 Vital Signs, Physical Findings, and Other Observations Related to Safety**

### **11.4.1 Vital signs**

Vital signs are assessed at all FEVs, MEVs, YEVs, EDVs, and at FV, and may also be assessed at Unscheduled Visits. Body weight is assessed at all FEVs, YEVs, EDVs, and at FV, and may also be assessed at Unscheduled Visits.

Observed values for SBP, DBP, pulse rate, and body weight will be summarized for Baseline, Study Entry, each visit during the Evaluation Period for which vital signs or body weight were assessed, EDV, Last Value, and FV. Changes from Baseline for SBP, DBP, pulse rate, and body weight will be summarized for all post-Baseline time points.

The number and percentage of subjects with an on-treatment PCST value, PCST low value, and PCST high value will be summarized for SBP, DBP, pulse rate, and body weight. This summary will consider all assessments after the first dose of BRV and prior to or on the date of the last dose of BRV.

Additionally, the number and percentage of subjects with a PCST value, PCST low value, and PCST high value will be summarized for the above parameters for Study Entry, each visit during the Evaluation Period for which vital signs or body weight were scheduled to be assessed, Last Value, EDV, and FV. Percentages will be relative to the number of subjects with a value at each time point.

PCST criteria (Section 13.3.4) are based on FDA Division of Neuropharmacologic Drug Products guidelines with some UCB-defined additions

### **11.4.2 Electrocardiograms**

ECGs are assessed at all YEVs, EDVs, and at FV, and may also be assessed at Unscheduled Visits.

The number and percentage of subjects with no abnormality, an abnormal but not clinically significant finding, and a clinically significant finding will be summarized overall. This summary will consider all assessments after the first dose of BRV and prior to or on the date of the last dose of BRV.

Additionally, the number and percentage of subjects with no abnormality, an abnormal but not clinically significant finding, and a clinically significant finding will be summarized for Baseline, Study Entry, each visit during the Evaluation Period for which an ECG is scheduled to be performed, Last Value, EDV, and FV. Percentages will be relative to the number of subjects with an ECG assessment at each time point. Subjects are counted at most once at each time point based on the worst observed outcome across all abnormalities reported at that time point.

A subject number listing will be provided that identifies subjects with a clinically significant finding after the first dose of BRV for each type of ECG abnormality.

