AED=antiepileptic drug; AV=Additional Visit; BRV=brivaracetam; CRF=Case Report Form; C-SSRS=Columbia Suicide Severity Rating Scale; DTP=Down-Titration Phone Call; ECG=electrocardiogram; EDV=Early Discontinuation Visit; EQ-5D=EuroQoL-5 Dimensions; EV=Entry Visit; FEV=Full Evaluation Visit; FV=Final Visit; HADS=Hospital Anxiety and Depression Scale; IEC=Independent Ethics Committee; IRB=Institutional Review Board; MEV=Minimal Evaluation Visit; QOLIE-31-P=Patient Weighted Quality of Life in Epilepsy Questionnaire; YEV=Yearly Evaluation Visit

- (a) Down-Titration Phone Call at the end of the Down-Titration Period is mandatory in case the subjects discontinue from more than 20mg/day BRV.
- (b) The following data will be obtained from the database of the Baseline Visit of the previous study and should not be recorded into the CRF: General Medical and Procedure History, AED History, and Epilepsy History.
- (c) The following data will be obtained from the database of the final visit of the previous study and should not be recorded in the CRF: Vital Signs, Weight, Physical Examination, Neurological Examination, ECG, Recording of seizures, Laboratory Assessment including Safety (blood chemistry, hematology, and urinalysis), concomitant AED plasma levels and BRV plasma levels.
- (d) Height will be recorded at Visit 1. Height will also be measured at each YEV and the FV for those subjects who are still potentially growing.

Table 5:1 Study Flowchart

	Entry Visit (EV)	Full Evaluation Visit (FEV)	Minimal Evaluation Visit (MEV)	Yearly Evaluation Visit (YEV)	Additional Visit (AV)	Early Discontinuation Visit (EDV) ^(l)	Down-Titration Phone Call (DTP) ^(a)	Final Visit (FV)	Reference to Section
ASSESSMENTS									

- ^(e) At FV, ECG is mandatory except if FV follows an EDV-where ECG results were normal.
- ^(f) QOLIE-31-P, EQ-5D, and HADS are to be completed at the beginning of the visit by all subjects who are not mentally impaired during the first 2 years.
- ^(g) Socio-professional data (to be collected during the first 2 years) will not be collected in [REDACTED]
- ^(h) Laboratory assessment includes blood chemistry, hematology, and urinalysis; where applicable (women of childbearing potential), a serum pregnancy test will be done. Laboratory is mandatory at FV except if FV follows an EDV where laboratory results were normal. Concomitant AED plasma levels and BRV plasma levels up to approval of Protocol Amendment 2.

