11.1.13 ECG

Following ethical approval of Protocol Amendment 2 and once the subject has signed the updated Informed Consent, the number of standard 12-lead ECGs will be reduced to once per year at each YEV and at the following visits: EDV and FV (in case the FV follows an EDV and the EDV ECG is normal, no additional ECG has to be performed at the FV).

At the EV, the ECG will be obtained electronically from the last Evaluation Visit of the previous study and should not be recorded in the CRF. The Investigator will determine whether the results of the ECG are normal or abnormal and assess the clinical significance of any abnormalities. The original ECG tracing will be signed or initialed and dated by the Investigator and retained as part of the source data.

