11.2.6 Down-Titration Phone Call

- Recording of adverse events.
- Reminder of appointment for the next visit according to the schedule described in Section 5.2.

11.2.7 Final Visit (FV following a Study Drug Free Period after an EDV or FV initiated upon Sponsor request at the end of the program)

- Vital signs including blood pressure and pulse.
- Body weight and height (only for those subjects still potentially growing).
- Physical and neurological examination.
- ECG (except if the FV follows an EDV where ECG results were normal).
- Retrieval of previous subject DRC.
- Recording of seizures.
- Laboratory assessment including safety (hematology, blood chemistry, and urinalysis); pregnancy test (if applicable); concomitant AED plasma levels and BRV plasma levels up to approval of Protocol Amendment 2 (except if the FV follows an EDV where laboratory results were normal).
- Recording of adverse events.
- Assessment of suicidality (C-SSRS).
- Medical procedures.
- Concomitant medications (AED and Non-AED) documentation.
- Drug return/accountability including study medication intake and compliance check.
- Completion of end of study status.
- Retrieval of "Clinical Study Subject Card".

The following assessments will be performed during the first 2 years:

- Healthcare provider consultation not foreseen by the protocol.
- Recording of workdays and schooldays lost and days subject received help from a caregiver (paid or not) at home.
- Hospital stay.
- Socio-professional data.

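### Final Visit ECG and laboratory results are summarised among those tested, but testing may be waived after a normal Early Discontinuation Visit, so the column leans toward abnormal subjects

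*SAP*

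**What the plan says.** Protocol Table 5:1, footnote (e), sets the ECG rule: "At FV, ECG is mandatory except if FV follows an EDV-where ECG results were normal". Section 11.1.13 repeats it as a permission: after a normal EDV tracing, "no additional ECG has to be performed at the FV". Footnote (h) sets the laboratory rule: "Laboratory is mandatory at FV except if FV follows an EDV where laboratory results were normal". The FV list in section 11.2.7 carries both exceptions, the laboratory one worded "except if the FV follows an EDV where laboratory results were normal".

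The SAP does not mention these waivers. Section 11.4.2 states that "ECGs are assessed at all YEVs, EDVs, and at FV", tabulates ECG categories at FV beside Baseline, Study Entry, scheduled visits and EDV, and fixes the denominator: "Percentages will be relative to the number of subjects with an ECG assessment at each time point". Section 11.3.1 does the same for potentially clinically significant (PCST) laboratory values: "Percentages for each parameter and time point will be relative to the number of subjects with a value at that time point". It also summarises observed values and change from Baseline at FV. Section 11.3.2 follows the same pattern for urinalysis. The missing-data section (4.2) deals with seizure diaries and dropouts only.

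**The concern.** For a subject who reaches FV through an EDV, being tested at FV depends on the earlier result of the very measure being tabulated. EDV-normal subjects can drop out of the FV denominator; EDV-abnormal subjects cannot. If abnormality persists at all, the percentage among those tested exceeds the percentage among everyone who attended.

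The EDV precedes down-titration, and the FV that follows it comes after 2 to 4 weeks off study drug. A reader who compares adjacent EDV and FV columns to see whether abnormalities resolve off brivaracetam could see a rise although no subject got worse. Vital signs and weight carry no waiver, so FV columns in different safety tables would describe different sets of subjects without saying so.

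**Working it through.** There is no figure in the plan to reproduce: all summaries are descriptive, and no sample size calculation was done. The check is a conditional-probability illustration. The documents give none of its five inputs, so all are assumptions:

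- a = proportion abnormal at EDV
- p11 = probability of abnormal at FV given abnormal at EDV
- p01 = probability of abnormal at FV given normal at EDV
- s = share of EDV-normal subjects who skip the test at FV
- u = share of FV attenders with no EDV, who must be tested, assumed to have the same overall rate T

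Rate if every FV attender were tested:

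T = a·p11 + (1−a)·p01

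Rate the SAP would report:

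R = [u·T + (1−u)·(a·p11 + (1−a)(1−s)·p01)] / [u + (1−u)·(a + (1−a)(1−s))]

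R exceeds T whenever s > 0, u < 1, 0 < a < 1 and p11 > p01. The two agree only if nobody skips, no FV follows an EDV, all subjects have the same EDV status, or FV status is unrelated to EDV status.

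**Worked case**, a = 20%, p11 = 50%, p01 = 5%: T = 0.20×0.50 + 0.80×0.05 = 14.0%.

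- All skip, every FV after an EDV: R = 0.10/0.20 = 50.0% (3.6x).
- 80% skip, every FV after an EDV: R = (0.10 + 0.80×0.20×0.05)/(0.20 + 0.80×0.20) = 0.108/0.36 = 30.0% (2.1x).
- 50% skip, every FV after an EDV: R = 0.12/0.60 = 20.0% (1.4x).
- All skip, 30% of FVs without an EDV: R = (0.30×0.14 + 0.70×0.10)/(0.30 + 0.70×0.20) = 0.112/0.44 = 25.5% (1.8x).

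Here the all-attender rate falls from 20% at EDV to 14% at FV. The planned table would show 20% followed by anything from 20% to 50%.

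**Range**, a = 5% to 30% with (p11, p01) = (70%, 5%), (50%, 5%), (30%, 5%) or (20%, 10%), as R/T:

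- All skip, every FV after an EDV: 1.5x to 8.5x. The top is a = 5%, p11 = 70%, p01 = 5%: 0.70/0.0825.
- 80% skip, every FV after an EDV: 1.2x to 2.5x.
- 50% skip, every FV after an EDV: 1.0x to 1.5x.
- All skip, 30% of FVs without an EDV: 1.1x to 2.0x.

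**Single laboratory parameters.** The waiver refers to the laboratory results as a whole, while PCST is judged parameter by parameter. Protocol 11.1.15 lists 15 chemistry, 13 haematology and 9 dipstick urinalysis items, 37 in all. Suppose each has a 5% chance of falling outside its reference range and 20 to 37 act as independent tests. The chance of an all-normal panel is then 0.95^20 = 36% to 0.95^37 = 15%, so 64% to 85% of subjects are retested. R/T cannot exceed 1 divided by the proportion retested: 1/0.64 = 1.6x to 1/0.85 = 1.2x. PCST limits such as 3 times the upper limit of normal also lie far from the reference limit, so the trigger predicts a given PCST value only weakly.

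**The case against.** The strongest reply is that this is a small matter of table labelling.

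- **The waiver permits omission; it does not forbid testing.** True, so the size depends on site practice.
- **Not every FV follows an EDV.** Section 11.2.7 also provides for an FV at the sponsor's request at the end of the program, and Table 5:1, footnote (i), separates completers from subjects who had an EDV. FVs without an EDV must include the tests and dilute the selection. Under footnote (l), subjects moving to another brivaracetam study or an access program have an EDV but may have no FV. This stands.
- **The laboratory effect is weak for any one parameter.** This stands if normal means every result within range. The protocol does not define it; if sites read it as not clinically significant, more subjects would skip and the cap above would rise.
- **Little rests on the FV column.** Reversal off drug is not a stated objective or variable, no testing is planned, counts appear beside percentages, and subject listings are provided. This lowers the stakes, but no table would tell the reader why the FV denominator is small or who is in it.

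A reader might infer a 3.3- to 10-fold inflation, from 1/a at EDV rates of 30% down to 10%. That is a ceiling. It needs every EDV-normal subject to skip, every FV to follow an EDV, and no abnormality to arise after a normal EDV. The documents support none of these. A reader might also take FV to be the only look at subjects off drug. It is the scheduled, summarised one after stopping, but unscheduled assessments are possible, and vital signs and weight are taken at FV without a waiver.

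**Conclusion.** The point holds for interpretation of the FV columns. Under the plan as written, FV percentages for ECG, laboratory PCST and urinalysis, and laboratory observed values and changes from Baseline at FV, come from a group selected on the EDV result. They are not comparable with EDV and will tend to overstate abnormality after brivaracetam is stopped. The direction needs only that some EDV-normal subjects skip and that abnormality persists to some degree.

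The size cannot be fixed from the documents. Under the assumed rates it is about 1.1x to 2.5x with 80% skipping or with 30% of FVs lacking an EDV, close to nil in the mildest 50%-skipping cases, and up to about 8.5x in the extreme case. It is clearest for ECG and weaker for single laboratory parameters.

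The documents do not support a wider conclusion that the trial's safety findings are compromised. The primary safety variables do not use these columns. The on-treatment PCST and ECG summaries and Last Value stop at the last dose. Vital signs and weight have no waiver.

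**What to change.** Amend SAP 11.3.1, 11.3.2 and 11.4.2:

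1. Present FV results in three groups: (a) FV without a preceding EDV, (b) FV after a normal EDV, (c) FV after an abnormal EDV. In each, give the numbers attending FV, tested and waived. State the waiver in the text and in a table footnote.
2. Do not show a pooled among-tested FV percentage beside EDV.
3. Add an EDV-to-FV shift table for subjects tested at both visits, with a note that retested EDV-abnormal subjects are subject to regression to the mean, so some apparent reversal is expected.
4. If an all-attender percentage is wanted, carry normal EDV results forward only as a labelled sensitivity figure. It assumes that nothing emerged after the EDV, which is part of what the FV is there to show.

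Deleting the FV column altogether is not advised, because it would discard FVs that were tested regardless of earlier results.

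The cost is SAP wording, one shift table per domain and a few more table rows. No new data are needed. With 108 subjects enrolled, some denominators will be small.
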